8.3.2.1. Categorical Response Variables

[Table 2](#) provides a list of each Clinical Measures of Severity item and the assessment scale for classifying overall response.

Table 2: Clinical Measures of Severity

Clinical Measures of Severity Item and Assessment Scale	Minimum change required for classifying overall response
Exophthalmos (measured in mm using the same Hertel exophthalmometer and same intercanthal distance for each individual subject)	Decrease \geq 2 mm
Lid aperture (distance between the lid margins in mm with the subject looking in the primary position, sitting relaxed and with distant fixation)	Decrease \geq 2 mm
Swelling of the eyelids (absent, mild, moderate, severe)	Decrease \geq One grade
Redness of the eyelids (absent, present)	Decrease \geq One grade
Redness of the conjunctiva (absent, present)	Decrease \geq One grade
Conjunctival edema (absent, present)	Decrease \geq One grade
Inflammation of the caruncle or plica (absent, present)	Decrease \geq One grade
Subjective diplopia score (0=no diplopia; 1=intermittent, i.e. diplopia in primary position of gaze, when tired or when first awakening; 2=inconstant, i.e. diplopia at extremes of gaze; 3=constant, i.e. continuous diplopia in primary or reading position)	Decrease \geq One grade
Eye muscle involvement (ductions in degrees)	Increase \geq 8° in at least one direction of gaze
Corneal involvement (absent/punctate keratopathy/ulcer)	Decrease \geq One grade

Clinical Measures of Severity Item and Assessment Scale	Minimum change required for classifying overall response
Optic nerve involvement (best corrected visual acuity, color vision, optic disc, relative afferent pupillary defect (absent, present), and visual fields if optic nerve compression is suspected).	Change of best corrected visual acuity by ≥ 2 lines on Snellen chart, or substantial color vision change, or significant change of visual fields, or significant change in optic disc appearance, or (Dis-) appearance of relative afferent pupillary defect

Response is assessed individually for each item.

Subjects who have a Study Baseline assessment on a particular measure for which improvement is not possible (i.e. they have the best possible assessment) will be considered to be a responder if they maintain the Study Baseline assessment. The analysis of optic nerve involvement will be generated only if at least 10% of the subjects have optic nerve decompression.

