10.6. OPTHALMIC EXAMINATION

A complete undilated ophthalmic examination will be performed as part of the physical examination. The ophthalmic exam should include best-corrected visual acuity, pupil exam, color vision assessment, Ishihara color plates (or equivalent) or related red desaturation, intraocular pressure and slit lamp exam. If significant abnormalities are noted compared with previous visits, including a loss of 2 lines or more of vision, development of pupil abnormalities including APD, rise in intraocular pressure, development of corneal infiltrates or other abnormalities not here specified but of concern to the ophthalmologist, further investigations of visual function will be conducted according to the ophthalmologist decision.

New findings reported from on-study ophthalmic examinations will not be reported as AEs if according to the investigator the abnormalities are related to TED and not related to the study drug.

For each of the assessments (pupil exam, color vision assessment, intraocular pressure, and slit lamp exam), shift tables will be presented providing the count of subjects with each type of finding (normal, abnormal - not clinically significant [NCS], or abnormal - clinically significant [CS]) at Study Baseline compared to each post-baseline visit by treatment received in HZNP-TEP-301 with percentages based on subjects with a non-missing value at the Study Baseline and post-baseline visit. In addition, a summary table will be provided for loss of 2 lines or more of vision (yes or no) including the count and percent of subjects at each post-baseline visit.

Similar summaries will be provided comparing to the HZN-001 Baseline.

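### The optic nerve response criterion states no direction, so applied literally it counts qualifying worsening as response, and the 10% condition for reporting the item uses a term that does not match it

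*SAP*

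**What the plan says.** Table 2 in SAP 8.3.2.1 lists eleven items. Its second column is headed "Minimum change required for classifying overall response", and the text below it adds "Response is assessed individually for each item". For optic nerve involvement the column gives alternatives, any one of which is enough: "Change of best corrected visual acuity by ≥ 2 lines on Snellen chart"; "or substantial color vision change, or significant change of visual fields"; "significant change in optic disc appearance, or (Dis-) appearance of relative afferent pupillary defect". Protocol Table 9.3 carries the same criterion.

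Two sentences under the SAP table qualify it:

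- **Maintenance rule.** A subject whose Study Baseline on an item leaves no room to improve counts as a responder by holding that level.
- **Reporting condition.** "The analysis of optic nerve involvement will be generated only if at least 10% of the subjects have optic nerve decompression". The item's own description mentions only suspected optic nerve compression, as the reason to assess visual fields.

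SAP 8.3.2.1 reports the count and percentage of responders on each item, for each eye, at Week 24 and by visit. SAP 10.6 gives a loss of two or more lines and a newly developed afferent pupillary defect as examples of significant abnormalities. It also tabulates the two-line loss at each post-baseline visit.

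**The concern.** A responder percentage is read as benefit. If the criterion accepts change in either direction, the optic nerve figure mixes recovery with deterioration, and the output does not separate them. The same eye could then be a responder in the efficacy tables and have a significant abnormality under SAP 10.6. Because each item is classified alone, no other item offsets the error.

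The reporting condition raises a second question. A programmer has to decide what decompression means before knowing whether to produce the table, and the answer may determine whether the item is reported at all.

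**Working it through.** The plan gives no figure to reproduce, so the check is a reading of the rules side by side.

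**Step 1. Direction of each row in Table 2.**

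- Decrease of at least 2 mm: exophthalmos, lid aperture (2 rows).
- Decrease of at least one grade: eyelid swelling, eyelid redness, conjunctival redness, conjunctival oedema, caruncle or plica inflammation, diplopia, cornea (7 rows).
- Increase of at least 8 degrees: ductions (1 row).
- No direction: optic nerve (1 row).

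2 + 7 + 1 + 1 = 11. Ten rows state a favourable direction and one states none. For the pupillary defect, the optic nerve row names both appearance and disappearance.

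**Step 2. What the rules do with each course.**

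| Optic nerve item at Study Baseline | Course | Row read literally | Maintenance rule | Improvement-only rule |
|---|---|---|---|---|
| Best possible | Unchanged | Not met | Response | Response |
| Best possible | Two-line loss or new defect | Response | Implies non-response | Non-response |
| Not best possible | Qualifying improvement only | Response | Silent | Response |
| Not best possible | Qualifying worsening only | Response | Silent | Non-response |
| Not best possible | One component better, another worse | Response | Silent | Non-response, if worsening takes precedence |
| Not best possible | No qualifying change | Non-response | Silent | Non-response |

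In the second line the two SAP rules conflict. In the fourth, nothing in the SAP stands against the literal row. An example is a subject with reduced acuity at baseline who loses two further lines.

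**Step 3. Size.** Let N be the subjects analysed, I those who only improve, M those who maintain a best-possible baseline, X those with mixed change, W those who only worsen from a baseline that is not best possible, and B those who worsen from a best-possible baseline.

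- Literal row plus maintenance rule: (I + M + X + W + B) / N.
- The same, if the maintenance rule is taken to override the row at a best-possible baseline: (I + M + X + W) / N.
- Improvement only, with worsening taking precedence: (I + M) / N.

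The excess is (X + W + B) / N or (X + W) / N, depending on the reading. M cancels from the difference but not from the reported rate. None of these counts is in the documents, and N is open as well, since SAP 3.5 does not base the sample size on statistical considerations. No percentage can be computed.

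**Step 4. The reporting condition.** The condition names decompression and the item names suspected compression. The condition gives neither a time point nor an eye. If it means surgery, Protocol Table 9.1 restricts eye surgery for thyroid eye disease, whether past or planned. Inclusion criterion 7 bars planned corrective surgery and any need for immediate surgical intervention. Few subjects could then count towards the 10%. Protocol 9.6.1.3 and 9.6.3.1 call for responder results on each component without this condition, and SAP Section 12 does not list it among the changes from the protocol.

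**The case against.** The strongest reply is that the intent is plain. Every other row points to improvement, and the maintenance rule makes sense only if response means improving or holding the best level. A subject who starts at the best level and develops a pupillary defect has not held it. This stands in part. A reader might infer that the SAP classes every deterioration as response, and the documents do not support that: at a best-possible baseline the two rules conflict, and the maintenance rule can reasonably be taken to prevail. But that rule adds a route to response and withdraws nothing from the row. It does not reach subjects who start below the best level.

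A reader might also attach a number by assuming counts of improvers and worseners. The documents supply none, and the reported rate would depend heavily on how many subjects maintain a best-possible baseline.

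Nor does it follow that the faulty rule is bound to be reported because the protocol has no 10% condition. Protocol 9.6 says that the SAP supersedes it, so the condition governs and the item may never be tabulated. In that case the row misclassifies nobody in a produced table.

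Finally, deterioration is not concealed. SAP 10.6 provides shift tables for pupil examination and colour vision and a table of two-line loss, and Listing 16.2.6.2.4.3 covers optic nerve data. This stands, although the 10.6 tables do not include optic disc or visual fields. Safety tables elsewhere also do not correct an efficacy percentage.

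**Conclusion.** The row and the reporting condition are both defective as written. Applied literally, the row accepts a loss of two or more lines, a worsening of colour vision, fields or disc, or a new pupillary defect as response. That contradicts the improvement meaning implied by the maintenance rule, and it contradicts SAP 10.6. The clearest misclassification is in subjects whose optic nerve baseline is not the best possible.

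The reporting condition does not match the item it controls, and it is not recorded as a change from the protocol. If it means surgery, it may rarely be met and the item would then go unreported; the documents do not show that it can never be met.

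The size cannot be stated. It depends on how many subjects worsen or have mixed change, on their baseline state, and on whether the reporting condition is met. The consequence is confined to one exploratory, descriptive item out of eleven. No primary or secondary endpoint uses this row.

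**What to change.** In SAP 8.3.2.1:

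1. Limit optic nerve response to improvement in a component: a gain of at least two lines, better colour vision, better fields or disc, or disappearance of the pupillary defect. State what makes a colour vision, field or disc change large enough to count.
2. Class any qualifying worsening as non-response, including mixed change and loss from a best-possible baseline. Tabulate it as a separate category.
3. Make the reporting condition match the item, for example optic nerve involvement at Study Baseline, and give its time point and eye; or remove the condition. If it is kept, record it in Section 12 as a change from the protocol.

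The cost is a few lines of SAP text and one added category in Table 14.2.7.1, with no new data collection. Protocol Table 9.3 can be aligned if the protocol is amended for other reasons; since the SAP governs the analysis, the SAP change is enough.

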8.3.2.2. Motility Restriction

Motility is examiner assessed by estimating the degrees of restriction in eye movements. Monocular excursions in horizontal and vertical directions of gaze are recorded using the light reflex (LR) ([Dolman et al, 2012](#)) test.

The clinician will shine a pen light in line with the eye being examined in ambient room light and observe the subject's eye along the light's axis. The subject will be asked to look in the four cardinal directions and the position of the light reflex is viewed on the surface of the cornea. If the light touches the limbus, the eye is assessed to be turned 45 degrees, if half way between the limbus and pupil edge, the eye is assessed at 30 degrees, and if it is at the pupil edge, it was assessed at 15 degrees. Intermediate ductions are judged by estimating the light position between these points to the nearest 5 degrees.

The monocular ductions of each eye (degrees) will be recorded for adduction, abduction, supraduction and infraduction.

Descriptive summaries of observed results and change from Study Baseline for the study eye and fellow eye will be provided for each motility measure by treatment received in HZNP-TEP-301 for the ITT Population at Week 24.

In addition, descriptive summaries for the study eye and fellow eye will be provided for each motility measure by treatment received in HZNP-TEP-301 for the ITT Population for each visit in the Treatment Period and for HZNP-TEP-301 proptosis non-responders in the Follow-Up Period.

8.3.3. CAS as a Continuous Variable

Descriptive summaries of CAS as a continuous variable and change from Study Baseline for the study eye and fellow eye will be provided by treatment received in HZNP-TEP-301 for the ITT Population at Week 24. In addition, descriptive summaries of CAS as a continuous variable for the study eye and fellow eye will be provided by treatment received in HZNP-TEP-301 for the ITT Population for each visit in the Treatment Period and for HZNP-TEP-301 proptosis non-responders in the Follow-Up Period.

8.3.4. Categorical Overall Response

To further explore the response based on both proptosis and CAS reduction, each subject will be classified into one of four response categories at Week 24:

- **High responders:** Subjects who had a reduction in both proptosis and CAS of 3 or more (≥ 3) from Study Baseline in the study eye, and no deterioration in the fellow eye (i.e., increase in CAS ≥ 2 points or increase in proptosis ≥ 2 mm).
- **Responders:** Subjects who had a reduction in both CAS and proptosis of 2 or more (but less than 3) from Study Baseline in the study eye, and no deterioration in the fellow eye.
- **Low Responders:** Subjects who had a reduction in both CAS and proptosis of 1 or more (but less than 2) from Study Baseline in the study eye, and no deterioration in the fellow eye.
- **Non-Responders:** Subjects who did not fit into any of the above categories, or were not present for the Week 24 evaluation

Descriptive summaries will be provided for both response definitions (study eye and fellow eye response) by treatment received in HZNP-TEP-301 for the count and percentage of subjects in each category for the ITT Population at Week 24.

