##### **9.6.3.2.1 Stratification of Proptosis and CAS Response into Four Responses Categories**

To further explore the response based on both proptosis and CAS reduction, each subject will be classified into one of 4 response categories at Week 24:

- High responders: Subjects who had a reduction in both proptosis and CAS of 3 or more ( $\geq 3$ ) from Baseline in the study eye, and no deterioration in the fellow eye (i.e., increase in CAS  $\geq 2$  points or increase in proptosis  $\geq 2$  mm).

- Responders: Subjects who had a reduction in both CAS and proptosis of 2 or more (but less than 3) from Baseline in the study eye, and no deterioration in the fellow eye.
- Low Responders: Subjects who had a reduction in both CAS and proptosis of 1 or more (but less than 2) from Baseline in the study eye, and no deterioration in the fellow eye.
- Non-Responders: Subjects who did not fit into any of the above categories, or were not present for the Week 24 evaluation.

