4.3. EXPLORATORY EFFICACY ENDPOINTS

Exploratory efficacy endpoints include:

1. The overall responder rate (percentage of subjects with ≥ 2 -point reduction in CAS AND ≥ 2 mm reduction in proptosis from Study Baseline, provided there is no corresponding deterioration [≥ 2 point/mm increase] in CAS or proptosis in the fellow eye) at Week 24.
2. Clinical Measures of Severity individual response status frequencies and percentage of responders for each component of clinical severity at Week 24.
3. Mean change from Study Baseline to Week 24 in the CAS.
4. Overall responder rate at Week 24 stratified by the level of response (high responders, responders, low responders, and non-responders; see Section 8.3.4 for definitions).
5. Mean change from Study Baseline to Week 24 in the GO-QoL questionnaire VF and A subscale scores.
6. Mean change from Study Baseline to Week 24 on the motility component of the Clinical Measures of Severity.

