8.3. EXPLORATORY EFFICACY ENDPOINTS AND ANALYSIS

8.3.1. CAS and Proptosis Categorical Response

The first exploratory efficacy endpoint is the overall responder rate, measured as the percentage of subjects with ≥ 2 -point reduction in CAS AND ≥ 2 mm reduction in

proptosis from Study Baseline, provided there is no corresponding deterioration (≥ 2 point/mm increase) in CAS or proptosis in the fellow eye at Week 24. Subjects missing the Week 24 evaluation will be considered to be treatment failures (non-responders) for the analysis. Only subjects with CAS > 1 and proptosis > 1 mm at Study Baseline in the ITT Population will be summarized.

Descriptive summaries of responder results for both study eye and fellow eye responder definitions will be provided by treatment received in HZNP-TEP-301 for the ITT Population at Week 24.

In addition, descriptive summaries of responder results for both study eye responder definitions (study eye responder and fellow eye responder) will be provided by treatment received in HZNP-TEP-301 for the ITT Population for each visit in the Treatment Period and for HZNP-TEP-301 proptosis non-responders in the Follow-Up Period, considering subjects missing the evaluations as treatment failures (non-responders). Similar summaries will also be provided separately by subject enrollment type (subjects who were proptosis non-responders in HZNP-TEP-301, subjects who relapsed during the Follow-Up Period in HZNP-TEP-301), tobacco use status (non-user, user), region (US, EU), and site.

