14.2.4.6.2	Proportion of Diplopia Sustained 0 by Visit (Study Eye)	ITT
14.2.4.6.3	Proportion of No Diplopia by Visit (Study Eye)	ITT
14.2.5.1	Summary and Change from Study Baseline in GO-QoL Overall Transformed Score by Visit	ITT
14.2.5.2	Summary and Change from Study Baseline in GO-QoL Overall Transformed Score by Visit, Subgroup Analysis by Tobacco Use Status	ITT
14.2.5.3	Summary and Change from Study Baseline in GO-QoL Overall Transformed Score by Visit, Subgroup Analysis by Enrollment Type	ITT
14.2.5.4	Summary and Change from Study Baseline in GO-QoL Overall Transformed Score by Visit, Subgroup Analysis by Region	ITT
14.2.5.5	Summary and Change from Study Baseline in GO-QoL Overall Transformed Score by Visit, Subgroup Analysis by Site	ITT
14.2.6.1	Proportion of Overall Responders by Visit (Study Eye and Fellow Eye)	ITT
14.2.6.2	Proportion of Overall Responders by Visit (Study Eye and Fellow Eye), Subgroup Analysis by Tobacco Use	ITT
14.2.6.3	Proportion of Overall Responders by Visit (Study Eye and Fellow Eye), Subgroup Analysis by Enrollment Type	ITT
14.2.6.4	Proportion of Overall Responders by Visit (Study Eye and Fellow Eye), Subgroup Analysis by Region	ITT
14.2.6.5	Proportion of Overall Responders by Visit (Study Eye and Fellow Eye), Subgroup Analysis by Site	ITT

14.2.6.6	Sustained Overall Response in the Follow-Up Period	Week 24 Overall Responders
14.2.7.1	Individual Clinical Measures of Severity by Visit (Study Eye and Fellow Eye)	ITT
14.2.8.1	Summary and Change from Study Baseline in Adduction, Abduction, Supraduction, and Infraduction by Visit (Study Eye and Fellow Eye)	ITT
14.2.9.1	Summary and Change from Study Baseline in CAS by Visit (Study Eye and Fellow Eye)	ITT
14.2.10.1	Proportion of Categorical Overall Response Status at Week 24 (Study Eye and Fellow Eye)	ITT
14.2.11.1	Summary and Change from Study Baseline in Transformed GO-QoL Score by Visit - Visual Functioning and Appearance	ITT
14.2.12.1	Investigator Assessment of Active Disease by Visit	ITT
14.2.13	Summary of Serum Concentrations of HZN-001 (ng/mL)	PK
14.3.1.1.1	Overall Summary of Treatment-Emergent Adverse Events During the Treatment Period	ITT
14.3.1.1.2	Overall Summary of Adverse Events During the Follow-Up Period	ITT
14.3.1.2.1.1	Treatment-Emergent Adverse Events by System Organ Class and Preferred Term During the Treatment Period	ITT
14.3.1.2.1.2	Adverse Events by System Organ Class and Preferred Term During the Follow-Up Period	ITT

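### The four-level response rule in SAP 8.3.4 codes some overall responders as Non-Responders, because both reductions must fall in the same band

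*SAP*

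**What the plan says.** SAP 8.3.4 places each subject in one of four categories at Week 24. All three response levels also require no deterioration in the fellow eye.

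- High: "Subjects who had a reduction in both proptosis and CAS of 3 or more".
- Responder: "a reduction in both CAS and proptosis of 2 or more (but less than 3) from Study Baseline in the study eye".
- Low: the same form of words, with both reductions at least 1 but below 2.
- Non-Responder: "Subjects who did not fit into any of the above categories, or were not present for the Week 24 evaluation".

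Protocol 9.6.3.2.1 uses the same bands; its Responder level is "a reduction in both CAS and proptosis of 2 or more (but less than 3) from Baseline in the study eye". Neither document gives a rule for reductions that fall in different bands.

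SAP 4.3 item 4 describes the endpoint as "Overall responder rate at Week 24 stratified by the level of response (high responders, responders, low responders, and non-responders"; that is, as a breakdown of the overall responder rate. Item 1 of the same section and SAP 8.3.1 define an overall responder by a CAS fall of at least 2 points and a proptosis fall of at least 2 mm, with no upper limit and no fellow-eye deterioration. SAP 8.3.1 adds a restriction: "Only subjects with CAS > 1 and proptosis > 1 mm at Study Baseline in the ITT Population will be summarized".

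The results go to two tables in SAP Section 16: Table 14.2.10.1, "Proportion of Categorical Overall Response Status at Week 24 (Study Eye and Fellow Eye"), and Table 14.2.6.1, "Proportion of Overall Responders by Visit (Study Eye and Fellow Eye").

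**The concern.** The upper limits on the Responder and Low levels apply to both measures, so a subject who does better on one measure than the other can drop out of every level. The residual category then labels that subject a Non-Responder.

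Two things are at stake. First, the categories are not ordered by improvement, which an analysis by level of response needs. Secondly, the two tables need not agree: one person can be an overall responder in Table 14.2.6.1 and a Non-Responder in Table 14.2.10.1, so High plus Responder need not add up to the overall-responder count that the endpoint is meant to break down.

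The entry criteria leave room for this. Protocol 9.3.1 admits non-responders on proptosis alone with no minimum CAS, and protocol 9.3.4 lets a relapse qualify on proptosis without the CAS criterion. Low CAS at Study Baseline is therefore possible, and that limits how far CAS can fall.

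**Working it through.** The plan gives no figure to reproduce. The check applies the written rule to possible pairs of reductions.

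**Inputs.** Let p be the proptosis reduction in mm and c the CAS reduction in points, both in the study eye, with no fellow-eye deterioration. CAS is the sum of seven items scored 0 or 1 (protocol Table 9.2), so c is a whole number of at most 7.

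**Rule as written (SAP 8.3.4).**
- High: p ≥ 3 and c ≥ 3.
- Responder: 2 ≤ p < 3 and 2 ≤ c < 3, so c = 2.
- Low: 1 ≤ p < 2 and 1 ≤ c < 2, so c = 1.
- Non-Responder: everything else.

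**Overall responder (SAP 4.3 item 1, 8.3.1).** p ≥ 2 and c ≥ 2.

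**Single cases.**

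| p (mm) | c (points) | Overall responder? | Level as written |
|---|---|---|---|
| 1 | 1 | No | Low |
| 2 | 2 | Yes | Responder |
| 2 | 3 | Yes | Non-Responder |
| 2 | 4 | Yes | Non-Responder |
| 3 | 2 | Yes | Non-Responder |
| 3 | 3 | Yes | High |

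The 2 mm/4 point subject is not High (2 < 3), not Responder (4 is not below 3) and not Low, and so ranks below the 1 mm/1 point subject.

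**All overall-responder pairs, whole mm, p from 2 to 6 (assumed cap), c from 2 to 7.** There are 5 × 6 = 30 pairs. High has p 3–6 and c 3–7: 4 × 5 = 20. Responder is the single pair (2, 2). The other 30 − 20 − 1 = 9 are coded Non-Responder: p = 2 with c = 3–7 (5 pairs) and p = 3–6 with c = 2 (4 pairs).

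**Other assumed grids.**

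| Grid | Pairs | High | Responder | Non-Responder |
|---|---|---|---|---|
| Whole mm, cap 4 | 3 × 6 = 18 | 2 × 5 = 10 | 1 | 7 |
| Whole mm, cap 6 | 30 | 20 | 1 | 9 |
| Whole mm, cap 8 | 7 × 6 = 42 | 6 × 5 = 30 | 1 | 11 |
| 0.5 mm steps, cap 6 | 9 × 6 = 54 | 7 × 5 = 35 | 2 | 17 |

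**By Study Baseline CAS.** CAS cannot fall by more than its baseline value b. With whole mm and cap 6 there are 5(b − 1) overall-responder pairs, of which 4(b − 2) are High and 1 is Responder. That leaves 5(b − 1) − 4(b − 2) − 1 = b + 2 coded Non-Responder:

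| b | 2 | 3 | 4 | 5 | 6 | 7 |
|---|---|---|---|---|---|---|
| Non-Responder / pairs | 4/5 | 5/10 | 6/15 | 7/20 | 8/25 | 9/30 |

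At b = 2, High is out of reach under any 3-point threshold. The fault is the reversal: if CAS resolves to 0, a 2 mm reduction is a Responder and a reduction of 3 mm or more is a Non-Responder.

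**The Low level.** With p from 1 to 6 and c from 1 to 7 there are 42 pairs. Of these, 42 − 30 = 12 have both reductions at least 1 but not both at least 2. Only (1, 1) is Low; the other 11 are Non-Responder.

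**Rule based on the smaller reduction.** With m = min(p, c), High is m ≥ 3, Responder 2 ≤ m < 3 and Low 1 ≤ m < 2. The 30 overall-responder pairs become 20 High and 10 Responder, with none coded Non-Responder. The 12 lower pairs all become Low.

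**The case against.** The strongest reply is that the limit of less than 3 was meant as not both at least 3, so that 2 mm/4 points is a Responder. The description in SAP 4.3 item 4 favours this, since only then do the levels break down the overall responder rate. The mock-ups are in a separate file, so the intended programming cannot be seen. But neither document states that reading, and the words put the limit on both reductions. If it was the intent, the text still needs correcting, because two programmers could produce different tables.

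Several narrower points stand:

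- The four categories are exhaustive, because the residual category takes everyone left over. The fault is who lands there.
- SAP 6.1 averages same-day values with no recorded time, so a CAS change could occasionally be fractional. A Responder CAS fall of exactly 2 is therefore the rule, with a rare exception.
- The grid counts are not patient frequencies, and the 11 of 12 Low pairs have no bearing on agreement between the two tables.
- This is one descriptive Week 24 table for an exploratory endpoint. The overall responder rate and the continuous proptosis and CAS results are reported separately, and no test depends on the classification.

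**Conclusion.** The concern holds on the text as written. Mixed-band reductions are coded Non-Responder even when the subject is an overall responder, the ordering is not monotone, and Tables 14.2.10.1 and 14.2.6.1 need not agree.

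In possible combinations, 9 of 30 overall-responder pairs are affected on the whole-millimetre grid capped at 6 mm; other assumed grids give 7 of 18, 11 of 42 and 17 of 54. The caps and the 0.5 mm step are assumptions. The share of subjects affected cannot be derived, because the documents give no distribution of CAS change.

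It should be fixed, but its reach is limited to the exploratory four-level table.

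**What to change.** In SAP 8.3.4, set the level by the smaller of the two reductions, keeping the requirement of no fellow-eye deterioration:

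- High: both reductions at least 3.
- Responder: both at least 2, but not both at least 3.
- Low: both at least 1, but not both at least 2.
- Non-Responder: all others, and subjects not present at Week 24.

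For the study eye, High plus Responder then equals the overall-responder count. The 8.3.1 restriction does not disturb this: a subject with study-eye CAS of 1 or less, or proptosis of 1 mm or less, cannot fall by 2 on both measures. Percentages can still differ, because 8.3.4 classifies every ITT subject, so use one denominator or footnote the difference.

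Apply the same rule to the fellow-eye definition, and state which eye the 8.3.1 restriction uses. If it is always the study eye, the fellow-eye counts may still disagree.

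Protocol 9.6 lets the SAP supersede, so the SAP edit with an entry in Section 12 is enough to take effect. Protocol 9.6.3.2.1 should be aligned too, through a formal amendment (protocol 9.7).

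The cost is one sentence per level and a footnote, ideally before programming, with no new data. The change can only move subjects up from Non-Responder, so record its date and reason as a clarification.
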